**Table 3-2 Study VX17-659-102: Treatment Period and Safety Follow-up Visit**

Event/Assessment a	Day 1	Day 15 (± 3 Days)	Week 4 (± 5 Days)	Week 8 (± 5 Days)	Week 12 (± 5 Days)	Week 16 (± 5 Days)	Week 20 (± 5 Days)	Week 24 (± 5 Days)	ETT Visit b	Safety Follow-up Visit 28 (± 7) Days After the Last Dose of Study Drug (If Applicable) c
Clinic visit	X	X	X	X	X	X		X	X	X
Telephone contact							X d			
Inclusion and exclusion criteria confirmation	X									
CFQ-R e	X		X	X	X	X		X	X	X
Weight and height f	X	X	X	X	X	X		X	X	X
Ophthalmologic examination								X g	X g	X g

a All assessments will be performed before dosing unless noted otherwise.

b If the subject prematurely discontinues study treatment, an ETT Visit should be scheduled as soon as possible after the decision to discontinue treatment. Subjects who prematurely discontinue treatment will continue to complete all scheduled study visits for assessments following completion of the ETT Visit (Section 9.1.4).

c The Safety Follow-Up Visit is required for all subjects, unless the subject completes the Week 24 Visit and has enrolled in a separate open-label study within 28 days after the last dose of study drug (Section 9.1.3). If an ETT Visit occurs 3 weeks or later following the last dose of study drug, then the ETT Visit replaces the Safety Follow-up Visit (Section 9.1.4).

d Telephone contact will be made to assess the subject’s status, any AEs, concomitant medications, treatments, and procedures.

e The CFQ-R, [REDACTED] must be completed before any other assessments scheduled at relevant visits. Refer to Section 11.6.3 and [REDACTED]

f Weight and height will be measured with shoes off. Following screening, height will be collected only for subjects ≤21 years of age on the date of informed consent.

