### **9.1.4 Early Termination of Treatment**

If a subject prematurely discontinues study drug treatment, an Early Termination of Treatment (ETT) Visit should be scheduled as soon as possible after the decision to discontinue treatment. Subjects who prematurely discontinue treatment will also be required to complete the Safety Follow-up Visit, approximately 28 days after their last dose of study drug. The assessments performed at the Safety Follow-up Visit are listed in [Table 3-2](#).

If the ETT Visit occurs 3 weeks or later following the last dose of study drug, then the ETT Visit will replace the Safety Follow-up Visit, and a separate Safety Follow-up Visit will not be required.

Subjects who prematurely discontinue study drug treatment will continue to complete all scheduled study visits for assessments following completion of the ETT Visit, as detailed in [Table 3-2](#). Data regarding concomitant antibiotic therapy for sinopulmonary signs/symptoms will also continue to be collected for these subjects.

If a subject withdraws from the study and also withdraws consent or assent, no further assessments will be performed. Vertex may retain and continue to use any data and samples collected before such withdrawal of consent or assent.

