## 12.3 Statistical Analysis

### 12.3.1 General Considerations

**Continuous variables** will be summarized using the following descriptive summary statistics: the number of subjects (n), mean, SD, median, minimum value (min), and maximum value (max). The precision of the measurement for each continuous variable will be specified in the SAP. Unless otherwise specified, min and max values will be reported with the same precision as the units of the raw data. The mean, median, and SD will be reported to 1 additional decimal place. Any values that require a transformation to standard units (metric or SI) will be converted with the appropriate precision.

**Categorical variables** will be summarized using counts and percentages. Percentages will be presented to 1 decimal place.

The **baseline value**, unless otherwise specified, will be defined as the most recent non-missing measurement (scheduled or unscheduled) collected before the first dose of study drug. For ECG, baseline will be defined as the most recent pretreatment measurement (or the average of triplicate measurements, if the most recent pretreatment measurement is obtained in triplicate) before the first dose of study drug.

**Absolute change** from baseline will be calculated as post-baseline value – baseline value.

The **Treatment-emergent (TE) Period** will include the time from the first dose of study drug in the Treatment Period (TC or Placebo) to 28 days after the last dose of the study drug or to the completion of study participation date (as defined in [Section 9.1.6](#)), whichever occurs first.

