### 9.1 General Considerations

The Schedule of Assessments is provided in Section 3 of CSP. The precision standards for reporting safety and efficacy variables are provided in an internal Biometrics document that specifies the programming rules including the precision for derived variables.

**Continuous variables** will be summarized using the following descriptive summary statistics: the number of subjects (n), mean, SD, median, minimum value (min), and maximum value (max).

**Categorical variables** will be summarized using counts and percentages. Percentages will be presented to 1 decimal place.

**Baseline value**, unless otherwise specified, is defined as the most recent non-missing measurement (scheduled or unscheduled) collected before the first dose of study drug in the Treatment Period.

**Absolute change** from baseline will be calculated as post-baseline value - baseline value.

**Relative change** from baseline will be calculated as (post-baseline value - baseline value)/baseline value.

**Treatment-emergent (TE) period** will include the time from the first dose of study drug in the Treatment Period until 28 days after the last dose of study drug or to the completion of study participation, whichever occurs first.

Completion of study participation for each individual subject is defined as one of the following:

- For subjects who complete the Treatment Period and enter an open-label study within 28 days of the Week 24 Visit: the Week 24 Visit
- For subjects who complete the Treatment Period and do not enter an open-label study within 28 days of the Week 24 Visit: the Safety Follow-up Visit
- For subjects who prematurely discontinue study drug treatment but do not withdraw consent (and assent, as applicable): the latest of the Week 24 Visit, Early Termination of Treatment Visit, or Safety Follow-up Visit (if required)
- For subjects who withdraw consent or assent: date of withdrawal of consent or assent, whichever is earlier (CSP Section 9.9)

If subjects are lost to follow-up (CSP Section 9.1.5), the date of completion of study participation will be defined as the date of the last contact.

**Unscheduled visits:** Unscheduled visit measurements will be included in analysis as follows:

- 1) In scheduled visit windows per specified visit windowing rules
- 2) In the derivation of baseline and last on-treatment measurements

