#### **9.4 Safety Analysis**

All safety analyses will be based on data from the TE period for all subjects in the Safety Set. Subjects will be analyzed according to the treatment they actually received in the Treatment Period. For subjects receiving study drug from more than one treatment group, the treatment group allocation will be the higher treatment group (VX-659/TEZ/IVA > TC Placebo).

The overall safety profile of the study drug will be assessed in terms of the following safety and tolerability endpoints:

- Treatment-emergent adverse events (TEAEs)
- Clinical laboratory values
- ECGs

- Vital signs
- Pulse oximetry

Only descriptive analysis of safety will be performed and no statistical testing will be performed.

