## 12 LIST OF APPENDICES

### Appendix A: Analysis Visit Windows for Safety and Efficacy Assessments

Table 12-1 Analysis Visit Windows for Safety and Efficacy Assessments			
Assessment	Visit	Target Study Day	Analysis Visit Window (in study days)
Safety Assessment			
Serum Chemistry Hematology Standard 12-lead ECG	Day 1 (Baseline)	1	≤1 Pre-dose
	Day 15	15	[1, 22]
	Week 4	29	(22, 43]
	Week 8	57	(43, 71]
	Week 12	85	(71, 99]
	Week 16	113	(99, 141]
	Week 24	169	(141, 183]
Safety Follow-up	Not applicable		Use nominal visit
Vital Signs	Day 1 (Baseline)	1	≤1
	Day 15	15	[1, 22]
	Week 4	29	(22, 43]
	Week 8	57	(43, 71]
	Week 12	85	(71, 99]
	Week 16	113	(99, 141]
	Week 24	169	(141, 183]
Safety Follow-up	Not applicable		Use nominal visit
Coagulation	Day 1 (Baseline)	1	≤1 Pre-dose
	Week 24	169	[1, 183]
	Safety Follow-up	Not applicable	Use nominal visit
Efficacy Assessment and Pharmacodynamic Assessment			
Spirometry	Day 1 (Baseline)	1	≤1 Pre-dose
	Day 15	15	(1, 22]
	Week 4	29	(22, 43]
	Week 8	57	(43, 71]
	Week 12	85	(71, 99]
	Week 16	113	(99, 141]
	Week 24	169	(141, 183]
Safety Follow-up	Not applicable		>183
Sweat Chloride	Day 1 (Baseline)	1	≤1 Pre-dose
	Week 4	29	(1, 43]
	Week 8	57	(43, 71]
	Week 12	85	(71, 127]
	Week 24	169	(127, 183]
CFQ-R	Day 1 (Baseline)	1	≤1
	Week 4	29	(1, 43]
	Week 8	57	(43, 71]
	Week 12	85	(71, 99]
	Week 16	113	(99, 141]
	Week 24	169	(141, 183]
	Safety Follow-up	Not applicable	

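### The treatment-emergent period closes 28 days after the last dose, but the Safety Follow-up Visit is on time up to day 35, so some on-schedule safety data reach listings only

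*SAP*

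**What the plan says.** **TE period.** In SAP 9.1 it starts at first dose and lasts "until 28 days after the last dose of study drug or to the completion of study participation, whichever occurs first". Protocol 12.3.1 agrees: "to 28 days after the last dose of the study drug or to the completion of study participation date". SAP 10.1.1 uses the same rule at the interim analysis and adds the data cutoff as a further limit.

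**Visit window.** The column heading in Protocol Table 3-2 reads "Safety Follow-up Visit 28 (± 7) Days After the Last Dose of Study Drug (If Applicable". Chemistry, hematology, coagulation, ECG, vital signs and pulse oximetry are all scheduled at that visit. Protocol 9.1.4 adds: "If the ETT Visit occurs 3 weeks or later following the last dose of study drug, then the ETT Visit will replace" the follow-up visit. No latest day is set for that replacement.

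**What the tables use.** SAP 9.4: "All safety analyses will be based on data from the TE period for all subjects in the Safety Set". Protocol 12.3.4 says the same. AE tables are confined to TEAEs (Protocol 12.3.4.1). SAP 9.4.2 to 9.4.5 restrict the laboratory, ECG, vital-sign and oximetry summaries, and the threshold and shift tables, to treatment-emergent data. An AE that begins or worsens later is classed as post-treatment and goes to a listing (SAP 9.4.1).

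**What points the other way.** The statistical part of the Protocol synopsis describes the safety endpoints as extending to the Safety Follow-up Visit. SAP Appendix A, Table 12-1, gives Safety Follow-up its own analysis visit for laboratory tests, ECG and vital signs, with the instruction "Use nominal visit" and no day limit. Neither place states an exception to the TE restriction.

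**The concern.** The schedule and the analysis period are both anchored at 28 days after the last dose, but only the schedule has a tolerance. A site can book the visit within the protocol's own window, collect a full safety panel, and find that none of it enters a by-arm summary because the visit fell on day 29 or later.

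The safety analysis is descriptive, so these tables are the between-arm safety comparison. A liver test or ECG value on day 27 counts toward the threshold tables, the shift tables and the plots of maximum liver values. The same value on day 31 does not. For completers who do not enter the open-label study, this visit is the only scheduled safety check off drug, because their last dose is taken the evening before Week 24.

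**Working it through.** **Step 1. Visit window (Protocol Table 3-2).** Earliest day 28 − 7 = 21 and latest day 28 + 7 = 35. Permitted days: 35 − 21 + 1 = 15.

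**Step 2. Which TE limit applies.** The TE period ends at the earlier of last dose + 28 days and completion of participation.
- For completers who "do not enter an open-label study within 28 days of the Week 24 Visit: the Safety Follow-up Visit" is the completion date. If that visit is on days 29 to 35, day 28 comes first and governs.
- For early stoppers who stay in the study, completion is the latest of the Week 24, ETT and follow-up visits (SAP 9.1). It cannot precede a follow-up visit on days 29 to 35, so day 28 governs again.
- Completers who enter the open-label study within 28 days have no follow-up visit and are not affected.

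**Step 3. Days beyond the cut.** Inside: days 21 to 28, 8 days. Outside: days 29 to 35, 7 days. 7/15 = 0.467. In study days, with the last dose on Day 168 (the evening before the Week 24 target of Day 169), the window is Day 189 to Day 203 and the TE period ends on Day 196.

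**Step 4. Share of on-time visits affected.** The documents give no distribution of visit days, so the timings below are assumptions. Normal timings are truncated to the window. Share = P(day 29 to 35) / P(day 21 to 35).

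| Assumed timing | Share after day 28 |
|---|---|
| Uniform over days 21–35 | 46.7% |
| Centred on day 28, SD 3 | 43.3% |
| Centred on day 28, SD 5 | 45.4% |
| Centred on day 26, SD 3 | 20.9% |
| Centred on day 30, SD 3 | 68.1% |

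**Step 5. Subjects, for scale only.** Assume that the 10% Week 24 dropout in Protocol 12.1 consists of early stoppers who all attend follow-up, and let r be the share of completers who roll over (not given). Subjects with a follow-up visit = 360 × [0.10 + 0.90 × (1 − r)].

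| r | Subjects with the visit | × 7/15 |
|---|---|---|
| 100% | 36 | 17 |
| 95% | 52 | 24 |
| 80% | 101 | 47 |
| 50% | 198 | 92 |

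Subjects who withdraw consent have no further assessments, so the early-stopper part is an upper figure.

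**Step 6. With a fixed 35-day limit.** All 15 permitted days satisfy day ≤ 35, so 0 of 15 fall outside, provided the completion date itself counts as inside the period.

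**The case against.** The best defence is that a fixed 28-day cut is a deliberate, exposure-based choice, stated identically in both documents and carried to the interim. That stands: a 28-day limit is not an error in itself. The fault is its mismatch with the permitted visit window and with the synopsis.

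A reader might also infer more than the documents support:

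- *That the follow-up visit is the only off-drug safety check for everyone affected.* It is so only for completers who do not roll over. Early stoppers have an ETT Visit as soon as possible and then continue the scheduled visits (Protocol 9.1.4), some of which may fall within 28 days of the last dose.
- *That Appendix A directly contradicts the TE rule.* Table 12-1 labels visits, while the TE period selects data. The nominal-visit instruction works without conflict for follow-up visits on days 21 to 28. What is missing is a statement of which rule is applied first. Without it, a programmer could place a day-32 value in a by-visit row but not in the threshold or maximum-value outputs.
- *That any AE reported at a late visit is excluded.* AEs are classified by onset or worsening. One that began by day 28 and was reported on day 33 remains a TEAE, and SAP Appendix E may impute an incomplete start date into the TE period.
- *That the data are lost.* They stay in subject listings, and SAEs and deaths have a separate listing that flags TEAE status.
- *That 47% is the expected loss.* It is the share of permitted days. It becomes a share of visits only if timing is uniform.

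**Conclusion.** The point holds as a mismatch between rules. Both documents end the TE period no later than day 28, both restrict safety summaries to that period, and the Protocol treats a visit on days 29 to 35 as on time while its synopsis carries the safety endpoints to that visit. On a literal reading, compliant late visits contribute nothing to the by-arm laboratory, ECG, vital-sign, oximetry, threshold and shift tables, and AEs with onset or worsening on those days are absent from the TEAE tables.

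The firm figure is 7 of 15 permitted days. The share of visits (about 21% to 68%) and the subject counts rest on assumed timing, dropout and rollover. No efficacy result, alpha or power figure is touched.

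**What to change.** **Preferred.** In Protocol 12.3.1, SAP 9.1 and SAP 10.1.1, end the TE period at a fixed 35 days after the last dose (28 plus the 7-day visit tolerance) or at completion of participation, whichever is earlier, with the data cutoff as a further limit at the interim. State that the completion date is included. A fixed limit is better than one tied to the actual visit date, which would let clinic booking set how far past day 28 the AE period runs.

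**Alternative.** Keep 28 days and add one by-arm summary of Safety Follow-up data, or of the ETT Visit that replaces it, collected after the TE period.

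**In either case.** State that the nominal-visit instruction in Table 12-1 is applied after the TE restriction. State also where a replacement ETT Visit after the cut is reported (listing or added summary), because with no latest day it can fall beyond day 35 as well. Bring the synopsis into line.

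**Cost.** One number in three places, or one descriptive table; no new data collection. Under the preferred option, up to 7 more off-drug days per subject count as treatment-emergent. The rule is the same in both arms, but the number of subjects contributing those days may differ by arm if discontinuation or rollover differs.

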## 9.2 Background Characteristics

### 9.2.1 Subject Disposition

The number of subjects in the following categories will be summarized:

- All Subjects Set
- Full Analysis Set

- Safety Set
- Randomized
- Randomized but not dosed

The number and percentage (based on the FAS) of subjects in each of the following disposition categories will be summarized by treatment group and overall:

- Completed treatment
- Prematurely discontinued treatment and the reason for discontinuation
- Completed study
- Prematurely discontinued the study and the reason for discontinuation
- Rollover to open-label study

A listing will be provided for subjects who discontinued treatment or who discontinued study with reasons for discontinuation.

### **9.2.2 Demographics and Baseline Characteristics**

Demographics and baseline characteristics will be summarized by treatment group and overall based on the FAS.

Demographic data will include the following:

- Age at baseline (in years)
- Sex (male, female)
- Ethnicity (Hispanic or Latino, not Hispanic or Latino, and not collected per local regulations)
- Race (White, Black or African American, Asian, American Indian or Alaska Native, Native Hawaiian or Other Pacific Islander, Other, and not collected per local regulations)
- Geographic region (North America, Europe [including Israel and Australia])

Baseline characteristics will include the following:

- Weight (kg)
- Height (cm)
- BMI (kg/m^2)
- BMI z-score (for subjects  $\leq 20$  years old at Baseline)

Stratification categories (in addition to sex) will include the following:

- Age at the Screening Visit (<18, and  $\geq 18$  years)
- ppFEV1 determined during the Screening Period (<70, and  $\geq 70$ )

Disease characteristics will include the following:

- ppFEV1 at baseline (<40,  $\geq 40$  to <70,  $\geq 70$  to  $\leq 90$ , and >90)
- ppFEV1 at baseline (continuous)

- Sweat chloride at baseline (continuous)
- CFQ-R respiratory domain score at baseline (continuous)
- Prior use of dornase alfa (Yes, No)
- Prior use of azithromycin (Yes, No)
- Prior use of inhaled antibiotic (Yes, No)
- Prior use of any bronchodilator (Yes, No)
- Prior use of any inhaled bronchodilator (Yes, No)
- Prior use of any inhaled hypertonic saline (Yes, No)
- Prior use of any inhaled corticosteroids (Yes, No)
- Infection with *Pseudomonas aeruginosa* within 2 years prior to screening (Positive, Negative)

In addition, data listings will also be provided for:

- Informed consent;
- Inclusion/Exclusion criteria violation for subjects with any such violations.

### 9.2.3 Medical History

Medical history will be coded by using the Medical Dictionary for Regulatory Activities (MedDRA). For the FAS, medical history will be summarized descriptively by system organ class (SOC) and preferred term (PT). The corresponding data listing will also be provided.

In addition, the number of subjects reported to have had positive cultures for respiratory pathogens within the 2 years prior to screening (i.e., answered yes on the respiratory microbiology form) will be summarized for the FAS. The corresponding data listing will be provided. Hospitalization and clinic visit history in the year prior to the signing of informed consent will be listed.

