**12.1 Sample Size and Power**

Approximately 360 subjects will be enrolled and randomized (1:1) to the VX-659/TEZ/IVA arm or the triple placebo arm. This sample size was determined to provide adequate power for the key secondary endpoint of number of PEx through Week 24. Information regarding the powering of primary and key secondary endpoints is provided below.

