### 7.2 Sample Size and Power

Approximately 360 subjects will be enrolled and randomized (1:1) to the VX-659/TEZ/IVA arm or the triple placebo arm. This sample size was determined to provide adequate power for the key secondary endpoint of the number of PEX through Week 24. Information regarding the powering of primary and selected key secondary endpoints is provided below.

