### **Power for Selected Secondary Endpoints**

A key secondary endpoint is the absolute change in ppFEV1 from baseline through Week 24. Assuming a within-group SD of 7 percentage points and a 10% dropout rate at Week 24, a sample size of 180 subjects in each treatment group will have approximately 99% power to detect a difference between the treatment groups of 5.0 percentage points for the absolute change in ppFEV1 from baseline through Week 24, based on a 2-sided, 2-sample *t*-test at a significance level of 0.05.

A key secondary endpoint is the number of PEx through Week 24. Assuming a rate of PEx for the placebo group of 0.6 over 24 weeks and a 10% dropout rate, with 180 subjects and the overdispersion parameter of 0.5 in each treatment group, the power to detect a 40% reduction in the PEx rate for VX-659/TEZ/IVA group compared to placebo group is approximately 80%, based on a 2-sided, 2-sample negative binomial regression model test for the ratio of rates, at a significance level of 0.05.

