### 9.3.2.2 Analysis Method

Absolute change in ppFEV1 through Week 24: Analysis of this variable will be based on an MMRM that is exactly the same as the primary efficacy variable. However, the Day 15 Visit will not be included in the estimation of the average treatment effect through Week 24 as the treatment effect is not expected to reach the steady state at Day 15.

Number of PEx through Week 24: Analysis of this variable will be performed using a negative binomial regression model with a fixed effect for treatment, as well as continuous baseline ppFEV1, age at screening (<18 versus ≥18 years of age), and sex (male versus female) as covariates. The logarithm of the subject-specific PEx analysis period duration (in years) will be treated as the offset in the model.

Absolute change in SwCl from baseline through Week 24: Analysis of this PD variable will be based on an MMRM similar to the analysis of the primary efficacy variable. Data obtained from Week 4, Week 8, Week 12, and Week 24 Visits will be included in the model and all of these visits will be included in the estimation of the average treatment effect through Week 24.

Absolute change in the CFQ-R respiratory domain score from baseline through Week 24: Analysis of this domain will be based on an MMRM similar to the analysis of the primary efficacy variable. Data obtained from Week 4, Week 8, Week 12, Week 16, and Week 24 Visits will be included in the model and all of these visits will be included in the estimation of the average treatment effect through Week 24.

Absolute change in BMI from baseline at Week 24: Analysis of this variable will be based on an MMRM similar to the analysis of the primary efficacy variable. Data obtained from Day 15, Week 4, Week 8, Week 12, Week 16, and Week 24 Visits will be included in the model.

Absolute change in SwCl from baseline at Week 4: Analysis of this PD variable will be based on an MMRM similar to the analysis of the primary efficacy variable. Data obtained from Week 4, Week 8, Week 12, and Week 24 Visits will be included in the model to estimate the treatment effect at Week 4.

Absolute change in CFQ-R respiratory domain score from baseline at Week 4: Analysis of this domain will be based on an MMRM similar to the analysis of the primary efficacy variable.

Data obtained from Week 4, Week 8, Week 12, Week 16 and Week 24 Visits will be included in the model to estimate the treatment effect at Week 4.

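### The PEx model that sized the trial at about 80% power leaves out the prior-year hospitalization history the trial collects: a missed, cheap efficiency option of unknown and at most modest gain

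*SAP*

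**What the plan says.** Both documents tie the sample size to PEx. Protocol 12.1 states: "This sample size was determined to provide adequate power for the key secondary endpoint of number of PEx through Week 24"; SAP 7.2 says the same.

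For the analysis, SAP 9.3.2.2 states: "Analysis of this variable will be performed using a negative binomial regression model with a fixed effect for treatment". The covariates are continuous baseline ppFEV1, age at screening (under 18 or not) and sex, with the log of the PEx analysis period as offset. Protocol 12.3.3.1.2 gives the same list. The SAP section on endpoints based on the number of clinical events (5.2.1) adds a Poisson fallback with the same covariates and offset, for use if the negative binomial model does not converge.

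On history before the trial, SAP 9.2.3 says: "Hospitalization and clinic visit history in the year prior to the signing of informed consent will be listed". In the visible text this history is not a stratification factor (Protocol 9.2, SAP 7.3), not in the baseline table (SAP 9.2.2) and not in any model.

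The multiplicity sections (Protocol 12.3.3.4, SAP 9.3.2.3) place PEx second among seven key secondary endpoints tested in fixed order.

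**The concern.** PEx has little power to spare and matters beyond itself. If it fails, five endpoints lose formal testing: sweat chloride and CFQ-R respiratory score through Week 24, BMI at Week 24, and sweat chloride and CFQ-R at Week 4.

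None of the three covariates in the model records a subject's past events. Hospitalization in the year before consent is a plausible predictor, and the protocol itself groups hospitalization for CF with PEx under events related to outcome (11.6.4). Treatment cannot affect it. In a log-link model with randomized treatment and no interaction, adding it leaves the rate ratio being estimated essentially unchanged; what may change is its precision. Any dispersion it explained would raise the chance of passing this step without more subjects.

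**Working it through.** **Inputs (SAP 7.2, power for selected secondary endpoints).** Rate and dropout: "Assuming a rate of PEx for the placebo group of 0.6 over 24 weeks and a 10% dropout rate". Size and dispersion: "with 180 subjects and the overdispersion parameter of 0.5 in each treatment group". The effect is a 40% reduction, so the active rate is 0.6 × 0.6 = 0.36. Test: "based on a 2-sided, 2-sample negative binomial regression model test for the ratio of rates, at a significance level of 0.05". Evaluable subjects per arm: 180 × 0.9 = 162.

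**Formula.** With dispersion k and n evaluable per arm:

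- Var(log RR) = (1/0.6 + 1/0.36 + 2k)/n
- power = Φ(|ln 0.6|/SE − 1.96)

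**The plan's own figure.** At k = 0.5 the bracket is 1.667 + 2.778 + 1.000 = 5.444. SE = √(5.444/162) = 0.1833. Then 0.5108/0.1833 − 1.96 = 0.827, and power is 79.6%. The stated figure of about 80% reproduces. Treating dropout instead as 90% mean exposure on 180 per arm gives 80.3%; a pooled null variance gives 81.0%. Ignoring dropout (83.6%) or reading 0.5 as the reciprocal of the dispersion (60.9%) does not match. Under the first formula, 80% power needs 183 randomized per arm against 180 planned, so there is no slack.

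**What a covariate could do.** It can reduce only the 2k term. The Poisson part, 4.444 of 5.444 (82%), stays whatever is adjusted for. Let f be the share of overdispersion removed, so k = 0.5(1 − f). The documents give no value for f; the range is an assumption.

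| f | k | SE | Power, 162 evaluable per arm | Randomized per arm for 80% |
|---|---|---|---|---|
| 0 | 0.50 | 0.1833 | 79.57% | 183 |
| 10% | 0.45 | 0.1816 | 80.30% | 179 |
| 20% | 0.40 | 0.1799 | 81.03% | 176 |
| 30% | 0.35 | 0.1782 | 81.77% | 173 |
| 50% | 0.25 | 0.1747 | 83.25% | 166 |
| 100% (ceiling) | 0 | 0.1656 | 86.95% | 149 |

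The last column is (1.960 + 0.842)² × (4.444 + 2k)/(ln 0.6)², rounded up, then divided by 0.9 and rounded up again.

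**Check by simulation.** With 1,500 runs per case and a lognormal covariate, unadjusted and adjusted power were 80.5% and 82.3% at f = 20%, and 81.9% and 85.0% at f = 50%. The gains of 1.8 and 3.1 points are similar in size to the formula's 1.5 and 3.7; the Monte Carlo error of each power is about √(0.8 × 0.2/1500) = 1.0 point.

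**The case against.** The strongest reply is that nothing here is wrong. The model is fully pre-specified and identical in the two documents. Its covariates are the three randomization factors, with ppFEV1 used continuously, and they match the primary MMRM. Another covariate list is a choice, not a correction. That stands, and the point is made only as an efficiency option.

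A reader might infer that the history is closely related to PEx, so that the plan gives up precision for free. The documents do not support that:

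- No section relates prior-year hospitalization to on-study PEx.
- It is a proxy. PEx is defined by antibiotic therapy, including oral and inhaled (SAP 9.3.2.1), and needs no hospital stay.
- The plan does not say whether k = 0.5 is before or after adjustment for ppFEV1, age and sex. If after, overlap with ppFEV1 would make f smaller.
- Neither a CF-specific field nor a count is shown to exist. Protocol 11.6.4.2 asks for reasons only for hospitalizations during the study.

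Nor is the change entirely without cost. The covariates are fixed in the protocol as well, so amending the SAP alone would create a discrepancy on a formally tested endpoint. A separate category for missing history could be sparse; with no events in it, its coefficient cannot be estimated under a log link. If the model then failed to converge, the Poisson fallback, which does not model overdispersion, would take over. The fix has to avoid this.

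It is also tempting to extend the covariate to the Cox model for time to first PEx. That endpoint is outside the testing sequence, so the same rationale does not apply, and an added covariate would change the conditional hazard ratio being estimated.

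Finally, several SAP efficacy sections are redacted and may hold supportive analyses. Absence can be stated only for the visible primary PEx model.

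**Conclusion.** The point holds as a minor, optional improvement. The visible primary PEx model sized the trial, has re-derived power of 79.6% and precedes five endpoints in the sequence, yet it does not use a baseline history that the trial collects and only lists. The treatment comparison is valid as planned.

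The gain is unknown. For an assumed f of 10% to 50% it is about 0.7 to 3.7 power points. Seen as sample size, f of 20% to 50% is worth roughly 7 to 17 randomized subjects per arm at 80% power (183 − 176 and 183 − 166). The ceiling is about 7.4 points, and no covariate would reach it. If the variable is uninformative, the gain is nil and the loss is about one degree of freedom. These figures rest on the plan's rates, dropout and dispersion, and on k = 0.5 being the dispersion left to explain.

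**What to change.** Before the interim data lock, add one binary covariate to the PEx model in SAP 9.3.2.2: any hospitalization in the year before consent, yes or no. Restrict it to CF hospitalizations only if the reason is recorded. Use the same term in the Poisson fallback, and make the same change in Protocol 12.3.3.1.2 so that the two documents agree. State a missing-history rule that keeps every subject without creating a sparse level, for example by assigning missing to the more common category. Leave the Cox model as it is.

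The timing allows this: SAP Section 4 has the SAP finalized before the interim data lock and provides for documented amendments, and PEx is formally tested only at the final analysis. The cost is one extra parameter, a matched protocol and SAP amendment, and reliance on a proxy. No new data collection is needed, provided that the history to be listed identifies hospitalization as such.
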